#### 2.5.1.2 Exclusion Criteria

- Be a user of topical ophthalmic products of any kind.
- Being a user of medicines, or herbal products, by any other route of administration.
- In the case of women: be pregnant, breastfeeding or planning to become pregnant within the study period.
- Have participated in clinical research studies 90 days prior to inclusion in the present study.
- Have previously participated in this same study.
- Be a user of contact lenses and cannot suspend their use during the study.
- They cannot follow the lifestyle considerations described in section 5.3.
- Having started the use of hormonal contraceptives or IUDs, 30 days prior to inclusion in the present study.
- Have a history of any chronic degenerative disease.
- Present inflammatory or infectious disease, active at the time of entry to the study.
- Present unresolved injuries or trauma at the time of study entry.
- Have a history of any type of eye surgery.
- Having undergone surgical procedures, not ophthalmological, in the last 3 months.
- Being or having an immediate family member (for example: spouse, parent / legal guardian, brother or child) who is part of the research site staff or the sponsor directly participating in this study.

#### 2.5.2 Elimination Criteria and Substitution of subjects

#### 5.2.1 Elimination criteria

- Withdrawal of the FCI letter.
- Presentation of a serious adverse event related or not to the investigational product, which at the discretion of the PI and / or the sponsor could affect the patient's ability to continue with the study procedures safely.
- Non-tolerability or hypersensitivity to any of the compounds used during the tests (fluorescein, green lysamine, tetracaine).
- Non-tolerability or hypersensitivity to any of the drugs under investigation.

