## 1.2 Study timeline

PROCEDURES	VB D 1	VF D 8 a +1	LLS D 10 ± 1
FCI signature	Х		
Clinic history	X		
Drug Evaluation	Х	X	
Concomitant	X	Х	
Urine pregnancy test	X	Χ	
MAVC	X	Χ	
Integrity of the ocular surface (Staining and evaluation of hyperemia and chemosis conjunctival)	Х	X	
Comprehensive ophthalmological evaluation	Х	X	
PIO	X	X	
Eligibility criteria	X		
EA evaluation	X	Χ	X
Research Product Allocation (PI)	Х		
Eye Comfort Index	X	Χ	
Delivery of the PI and start of intervention	Х		
Subject's Daily Delivery	X		
Assessment of adherence		Х	
Return / Evaluation of Subject Diary		X	
Return of PI		X	

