#### 2.3.2 Specific objectives

- Compare the safety of the Lagricel® Ofteno multi-dose formulation against Lagricel®
   Ofteno unit doses manufactured by Sophia Laboratories S.A. of C.V. through the incidence
   of AD.
- Compare the tolerability of the Lagricel® Ofteno multi-dose formulation against Lagricel®
   Ofteno unit-dose manufactured by Sophia Laboratories S.A. of C.V. using the ICO score.

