#### 2.5.5 Recruitment and retention strategies

This is a phase I study, which is planned to be conducted in 1 center. The selected center will be responsible for the recruitment of the subjects.

The minimum expected recruitment rate is 0.37 subjects per day.

The duration of the subject's participation in the study is approximately 10 days, during which they will only have to attend one visit after the baseline, so no retention problems are anticipated. However, the subjects will be creditors of a travel allowance for transportation and to fulfill their visits. Other strategies to improve subject retention include, but are not limited to:

- Clearly report the importance of the study and the benefits that the population will obtain from its results.
- Make calls or send text messages to remember appointments or activities to do.
- Provide a printed calendar and an identification card in order to remember appointments and activities to be carried out, in addition to the estimated time of their duration.
- Offer flexible service hours.
- Systematic organization of the study procedures, so that the subject does not last longer than necessary during his visit.
- Minimize the waiting times of the subject. All the materials to be delivered to de subject or recruitment strategies implemented by the Centers, will be submitted for approval by the corresponding committees.

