#### 2.5.6 Procedure in case of loss of follow-up

For this protocol, loss to follow-up is defined as those subjects who were randomized, who were active subjects in the study at some point, but their final evaluation could not be completed.

In the event that the participating subject does not attend their appointment, the research center must make a call to find out the reason and will try to make a new appointment within the established window period or an unscheduled appointment. In the event that it is not possible to make an appointment, the presence of adverse events and the reason for leaving the study will be asked, as minimal data.

It is considered that a loss to follow-up <10% does not represent a problem for the validity of the results obtained. [27, 28]

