#### 7.3 Outcomes Variables

#### 7.3.1 Primary outcome Variables

- Incidence of adverse events (AE) (Evaluation Time: day 8 and 10).
- Score of the Ocular Comfort Index (ICO) (TE: day 8).

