#### 7.4.2 Unscheduled follow-up visits

At the request of the patient or any other individual related to the study, unscheduled follow-up visits may be carried out to report adverse events. During these visits, all pertinent data on reported adverse events should be collected and, where appropriate, an appropriate management plan should be established.

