#### 10.1.3 Procedure for handling missing data

The safety evaluation will include in the analysis all those subjects (both eyes), who have been exposed at least once to any of the interventions, regardless of the visit in which they were eliminated from the study (ITT, intention-to-treat population).

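### Subjects eliminated for not tolerating a study product can drop out of the primary tolerability (ICO) comparison, because no ICO is required at elimination and no rule covers a missing one

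*Combined protocol and SAP*

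**What the plan says.** All references are to the Combined protocol and SAP.

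- Section 5.2.1 lists "Non-tolerability or hypersensitivity to any of the drugs under investigation" among the elimination criteria. Non-tolerability is not defined further.
- Section 2.3.2 makes the tolerability comparison against Lagricel® "Ofteno unit-dose manufactured by Sophia Laboratories S.A. of C.V. using the ICO score". Section 7.3.1 lists "Score of the Ocular Comfort Index (ICO) (TE: day 8") as one of two primary outcomes; the other is AE incidence.
- The timeline in section 1.2 has the row "Eye Comfort Index X Χ", marked at the baseline and final visits and not at the day-10 safety call. Section 2.5.5 tells subjects "they will only have to attend one visit after the baseline".
- Under section 7.4.2, "unscheduled follow-up visits may be carried out to report adverse events". Under section 2.5.6, if a missed appointment cannot be rebooked, "the presence of adverse events and the reason for leaving the study will be asked, as minimal data". Neither section mentions the ICO.
- Section 10.1.3, on missing data, keeps every exposed subject in the safety evaluation "regardless of the visit in which they were eliminated from the study". It says nothing about a missing ICO score.
- Section 10.1.5 limits the analysis for the study objective to diary adherence of at least 75%. It calls the product safe and effective if no primary outcome differs between the arms.

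**The concern.** A subject who cannot tolerate the drop has the worst tolerability result that the trial can produce. Under the plan that subject may have no value on the tolerability measure. The missingness then depends on the outcome itself. The arm with more intolerance loses its worst scores and comes to resemble the other arm.

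In a trial that set out to show a difference, this loss would work against the sponsor. Here success is the absence of a difference, so the loss moves the ICO result towards success. Once a subject has left without an assessment, the score cannot be recovered.

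**Working it through.** **1. The plan's own figures.** The plan gives no expected elimination rate and no ICO mean or standard deviation. The only related figure is the 20% loss allowance in section 10.2.2: 14 × 1.2 = 16.8, rounded to 17 per arm. That leaves room for 17 − 14 = 3 losses per arm. It covers how many subjects are lost, not why.

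**2. Adherence filter.** Four applications a day for 7 days (section 2.6.1.3) make 4 × 7 = 28 indicated applications, and 0.75 × 28 = 21. Five full days give 5 × 4 = 20. If the denominator is the full course, a subject stopped before the first application of day 6 also fails section 10.1.5. For such a subject an ICO at elimination would still not enter the objective analysis. (Section 6.4 uses 70%, or 19.6 applications, for its efficacy analysis; that conflict is a separate matter.)

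**3. Illustration of the effect.** All of the following is assumed: m of 17 test subjects and 0 of 17 controls are eliminated for intolerance, and ICO scores follow the same distribution in everyone else.

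- Probability that a random test subject scores worse than a random control, with eliminated subjects ranked worst: [(17 − m) × 0.5 + m] / 17. For m = 5 this is (6 + 5) / 17 = 0.647. In completers it is 0.50.
- Two-sided Fisher p for m/17 v 0/17: 2 × C(17,m) / C(34,m) for m ≥ 2. For m = 5 this is 2 × 6,188 / 278,256 = 0.044.
- Rejection rates: two-sided Mann-Whitney test at 0.05, normal scores (mean 30, SD 10, assumed), 3,000 simulated trials per row.

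| m eliminated (test arm) | P(test worse), worst rank | Fisher p | Rejects, completers only | Rejects, worst rank |
|---|---|---|---|---|
| 0 | 0.500 | 1.000 | 4.5% | 4.5% |
| 1 | 0.529 | 1.000 | 4.8% | 4.7% |
| 2 | 0.559 | 0.485 | 4.2% | 6.9% |
| 3 | 0.588 | 0.227 | 4.6% | 11.0% |
| 4 | 0.618 | 0.103 | 5.0% | 17.1% |
| 5 | 0.647 | 0.044 | 5.1% | 25.9% |
| 6 | 0.676 | 0.018 | 4.4% | 40.9% |

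A second simulation with skewed (gamma) scores and 4,000 trials gave 4.2% v 17.2% for m = 4 and 4.8% v 25.6% for m = 5, so the shape of the distribution matters little.

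**4. Reading the table.** The completers-only column stays at the chance level by construction, because completers were assumed alike. What it shows is that the planned ICO test does not respond to m. With one or two eliminations the worst-rank analysis hardly differs either. If both arms lose the same number, the comparison is not tilted, by symmetry.

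**The case against.** The strongest reply is that these subjects are not lost to the trial. AE incidence is also a primary outcome. Section 7.3.3.1 lists burning, irritation and foreign body sensation as expected AEs. Section 8.4 requires AEs to be verified by questioning, diary and examination and followed to their outcome. Section 10.1.3 keeps every exposed subject, and section 10.1.5 requires no difference on all primary outcomes. This stands. A reader might infer that intolerance disappears from the decision, and the documents do not support that. The reply does not close the gap, however. Section 2.3.2 assigns tolerability to the ICO, and a present/absent AE count treats a brief sting and an elimination alike.

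A reader might also infer that eliminated subjects get no closing assessment, or that the ICO is measured only in people who tolerated the drop. Both go too far. Nothing bars an eliminated subject from the final visit, unscheduled visits collect AE data, and subjects with discomfort who are not eliminated still complete the ICO. The gap is one of silence: an ICO at elimination is not required.

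Finally, few eliminations may occur. Section 2.2.4 states that the two formulations are identical, and section 7.3.3.1 expects mild reactions lasting no more than 30 seconds. This also stands, and it limits the likely size.

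**Conclusion.** The point holds as a gap in how one of the two primary outcomes is ascertained and analysed. Subjects eliminated for product intolerance can be absent from the ICO comparison for an outcome-related reason. If intolerance differs between arms, their absence pulls the ICO result towards no difference, which is the success criterion.

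The size cannot be calculated from the documents. The 5/17 v 0/17 case is illustrative and should not be read as a forecast; it is also where the Fisher p first falls below 0.05 (4/17 gives 0.103). The direction rests on two assumptions: that eliminated subjects would have scored worse than completers, and that eliminations are unequal between arms.

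A reader might further infer that intolerant subjects would be replaced by tolerant ones. Section 5.3.1 provides replacement for consent withdrawal and loss to follow-up, and does not name intolerance. The definition of loss in section 2.5.6 is wide enough to leave this unclear, but the documents do not say it will happen.

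This should be fixed, since the remedy is cheap. It does not by itself invalidate the trial.

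**What to change.** Leave the elimination rule unchanged and amend the measurement and analysis text.

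1. Report the number eliminated for product non-tolerability, by arm, beside the ICO result as part of the tolerability outcome.
2. Add a stated sensitivity analysis of the ICO Mann-Whitney test in all exposed subjects, whatever their adherence, with subjects eliminated for product non-tolerability given the worst rank. Unless the adherence cut-off is set aside here, worst rank has no effect for anyone stopped early.
3. For these subjects, where consent remains, bring forward the final-visit ICO and other final-visit assessments, omitting any procedure whose compound caused the elimination. Report the early ICO descriptively only. The questionnaire (Annex 15.1) asks about the past week, so after two days of treatment it would cover about five pre-treatment days.

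The cost is wording in the protocol and analysis plan, one brought-forward visit for a few subjects, and a little extra analysis. No new procedure is needed.

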#### 5.3.1 Subtitution of sujects

The sponsor, with prior authorization from the research ethics committees, may decide to replace the subjects who withdraw their CRF or those who present loss of follow-up, in case it is necessary to balance the study groups so that they are evaluable.

#### 2.5.3 Lifestyle considerations

For the study, participants may have to modify some lifestyle activities to meet the following:

- Refrain from tobacco use.
- Refrain from the use of electronic vaporizers.
- Avoid submerging in water without eye protection (goggles-protective glasses).
- Avoid direct exposure to fans (including air conditioning vents) during activities involving sight. 24 hours before your review visits.
- Maintain your sleep-wake cycle with which you enter the study.

#### 2.5.4 Counting failures

A scrutiny failure is defined as those participants who agree to participate in the study, giving their consent, but who are not assigned to a treatment group, that is, they do not enter the study. The following information on scrutiny failures must be reported at a minimum:

- Demographic data.
- Details of the scrutiny failure (specify if it is due to the eligibility criteria, to which, or some other reason for the failure).
- Presence of serious adverse events during the scrutiny.

This is necessary to comply with the CONSORT (Consolidated Standards of Reporting Trials) guidelines for the publication of results or to answer possible questions from the regulatory authorities.

Subjects who do not meet the eligibility criteria to participate in the study due to a specific modifiable factor may be eligible for re-scrutiny. Subjects in this case must use the same initial scrutiny number.

#### 2.5.5 Recruitment and retention strategies

This is a phase I study, which is planned to be conducted in 1 center. The selected center will be responsible for the recruitment of the subjects.

The minimum expected recruitment rate is 0.37 subjects per day.

The duration of the subject's participation in the study is approximately 10 days, during which they will only have to attend one visit after the baseline, so no retention problems are anticipated. However, the subjects will be creditors of a travel allowance for transportation and to fulfill their visits. Other strategies to improve subject retention include, but are not limited to:

- Clearly report the importance of the study and the benefits that the population will obtain from its results.
- Make calls or send text messages to remember appointments or activities to do.
- Provide a printed calendar and an identification card in order to remember appointments and activities to be carried out, in addition to the estimated time of their duration.
- Offer flexible service hours.
- Systematic organization of the study procedures, so that the subject does not last longer than necessary during his visit.
- Minimize the waiting times of the subject. All the materials to be delivered to de subject or recruitment strategies implemented by the Centers, will be submitted for approval by the corresponding committees.

#### 2.5.6 Procedure in case of loss of follow-up

For this protocol, loss to follow-up is defined as those subjects who were randomized, who were active subjects in the study at some point, but their final evaluation could not be completed.

In the event that the participating subject does not attend their appointment, the research center must make a call to find out the reason and will try to make a new appointment within the established window period or an unscheduled appointment. In the event that it is not possible to make an appointment, the presence of adverse events and the reason for leaving the study will be asked, as minimal data.

It is considered that a loss to follow-up <10% does not represent a problem for the validity of the results obtained. [27, 28]

#### 2.5.7 Identification of the subject

The study subjects will be identified by a number and the initials of their name.

The initials of the study subject will be obtained starting with the first letter of the name, followed by the first letter of the first surname and the first letter of the second surname, obtaining a maximum of three letters, in the event that the person has two names or a compound surname always the first letter will be used.

#### Example:

- A. Arieh Daniel Mercado Carrizalez
  - a. Initials: AMC

B. Juan De la Torre Orozco b. Initials: JDO

In the scrutiny stage (within the baseline visit) the participant number will be assigned consecutively, using 3 consecutive digits. Once the subject has been selected, he will be assigned a number with which he will be identified throughout the study. This code will be made up of eight numbers in the following order from left to right:

- three digits of the molecule under study according to the name by the sponsor.
- two digits corresponding to the research center number...
- three digits of the consecutive number assigned to their inclusion in the research

#### center.

#### Example:

## 2.6 Investigational product

#### 2.6.1 Managed Products

#### 2.6.1.1 Investigational Product

- Generic name: Sodium Hyaluronate
- Distinctive name: Lagricel® Ofteno multi-dose (PRO-037)
- Active principles: Sodium Hyaluronate 0.4%.
- Excipients: sodium chloride, monobasic sodium phosphate monohydrate, anhydrous dibasic sodium phosphate, water for the manufacture of injections.
- Pharmaceutical form: Ophthalmic solution
- Presentation: multi-dose dropper bottle.
- Prepared by: Sophia Laboratories S.A. of C.V.
- Description of the solution: clear solution, free of visible particles.
- Description of the container: White bottle with a capacity of 10 mL, made of low-density polyethylene.

#### 2.6.1.2 Reference product

- Generic name: Sodium Hyaluronate
- Distinctive name: Lagricel® Ofteno unit dose
- Active principles: Sodium Hyaluronate 0.4%.
- Excipients: sodium chloride, monobasic sodium phosphate monohydrate, anhydrous dibasic sodium phosphate, water for the manufacture of injections.
- Pharmaceutical form: Ophthalmic solution
- Presentation: Single dose vial.
- Prepared by: Sophia Laboratories S.A. of C.V.
- Description of the solution: clear solution, free of visible particles.
- Description of the container: transparent vial with a capacity of 0.5mL.

#### 2.6.1.2.1 Justification of the reference product

Lagricel® Ofteno unit dose is a commercially available lubricant, with a previously described safety and efficacy profile.

#### 2.6.1.3 Dosage of Investigational Products

One drop four times a day, both eyes, for 7 days.

#### 2.6.1.3.1 Dose justification

Ophthalmic lubricants are generally prescribed as needed (pro re nata [PRN]). [29] However, the study by Asbell et al compared the efficacy of QID versus PRN. Their results showed that, although there was no difference in clinical signs, the QID group had greater improvement in symptoms. [30] For this reason it is proposed as a posology for this study.

#### 6.2 Storage and handling of research products in the study center.

The delivery will be made by means of a courier service hired by the sponsor, expressly selected for this purpose, to the address of the research center according to the study plan.

The reception will be carried out by the assigned personnel of the investigation team. You must verify the good condition of the primary packaging (box). In the event that it shows alterations or defects in its integrity that from its judgment could have damaged the content, it must report it to the sponsor. If the package does not show significant defects, proceed to open it.

Inside you must locate the acknowledgment of receipt document and the temperature data logger. You should check that the registered temperature complies with what is specified for transport and storage. It will verify the content (PI) with what is reported in the document. In case the document corresponds with the content, they will sign the receipt and send it to the sponsor. Otherwise, it will notify the sponsor.

Storage and protection is the responsibility of the research center. The medicine must be kept in a secure area with restricted access.

The storage temperature should be no more than 30 ° C.

The research center is obliged to record, in the designated format, the temperature recorded in the data logger, every day while the protocol is in force and has PIs. Said data will be reviewed by the clinical monitor according to the record in the data logger.

In the event of material loss, it must be documented in the entry and exit log together with a clear description of the mechanism by which the loss occurred.

Upon completion of the protocol, all study material will be retrieved by the sponsor as part of the closing audit. The final delivery of material will be made by the principal investigator or the person designated by him to deliver the material at the end of the study.

The sponsor reserves the right to initiate civil and criminal actions against the principal investigator in the event of a lack of undocumented material at the end of the study.

#### 6.3 Unauthorized concomitant treatments and medications during the study

The use of concomitant medications by any route of administration will not be allowed during the intervention period. Except those specified for the study procedures. The objective of this restriction is to avoid pharmacological interactions that could alter the results of the variables evaluated. Allowed drugs:

- Ophthalmic:

o Tetracaine 0.5%

